5. SAMPLE SIZE JUSTIFICATION

A total of up to 24 subjects with renal impairment (up to 8 subjects with severe impairment, and, if necessary, up to 8 subjects with moderate impairment, and/or up to 8 subjects with mild impairment, per eGFR using the CKD-EPI equation) and approximately 8 to 24 matched-control healthy subjects with normal renal function will be enrolled in the study with the goal of having at least 6 subjects from each renal impairment group enrolled in the study and at least 6 subjects with normal renal function complete the study. The sample size chosen for this study was based upon precedent set by other PK studies of similar nature and

was not based on power calculations to detect statistically significant differences among groups. This number is considered a sufficient sample size to evaluate the PK of LOXO-305 under various degrees of renal function.

6. STUDY TREATMENT AND RENAL FUNCTION GROUPS

The planned treatment administered for all subjects will be 200 mg LOXO-305.

The renal function group names and ordering to be used in the TFLs are presented in Table 2.

Renal Function Group	Abbreviation	Order in TFLs
Normal Renal Function	Normal	1
Mild Renal Impairment	Mild	2
Moderate Renal Impairment	Moderate	3
Severe Renal Impairment	Severe	4

All renal function groups described above are the planned groups. If the mild and moderate renal impairment groups are not enrolled, the subsequent order of the severe group will be amended. The TFLs will reflect the actual renal function groups dosed based upon their eGFR using the CKD-EPI equation.

7. DEFINITIONS OF POPULATIONS

Any protocol deviations, including those related to SARS-CoV-2 (COVID-19), will be considered prior to database lock for their importance and taken into consideration when assigning subjects to populations.

7.1. All Subjects Population

The all subjects population will include all subjects who signed the ICF and had any study assessment recorded in the database per the protocol.

7.2. Safety Population

The Safety Population will include all subjects who received 1 dose of study drug. Subjects will be classified into renal function groups based off of their baseline eGFR value using the CKD-EPI equation.

7.3. Pharmacokinetic Population

The PK Population will include all subjects who received a dose of LOXO-305, have at least 1 quantifiable plasma concentration, and for whom at least 1 PK parameter can be computed. A subject may be excluded from the PK summary statistics and statistical analysis if the subject has an AE of vomiting that occurs at or before 2 times median t_{max} . The impact of protocol deviations on the PK population will be evaluated on a case-by-case basis.

8. STATISTICAL METHODOLOGY

8.1. General

Listings will be provided for all data captured in the database. Listings will include all subjects assigned to the all subjects population and include data up to the point of study completion or discontinuation. Subjects are generally considered to have completed the study if they completed all protocol-specified procedures and assessments for the EOS visit. Any subject who discontinued the study will be identified accordingly in the listings. Summaries and statistical analyses will include the subjects assigned to the relevant population based on data type.

Data analysis will be performed using the SAS[®] statistical software package Version 9.4 (or higher if upversioned during the study).

Analysis Data Model (ADaM) datasets will be prepared using Clinical Data Interchange Standards Consortium (CDISC) ADaM Version 2.1 (or higher if upversioned during the study) and CDISC ADaM Implementation Guide Version 1.2 (or higher if upversioned during the study). Pinnacle 21 Community Validator Version 3.1.0 (or higher if upversioned during the study) will be utilized to ensure compliance with CDISC standards.

Caution should be used when interpreting results from the statistical analyses conducted in this study because the sample size is not based on power calculations.

Where reference is made to 'all calculations', this includes, but is not limited to, summary statistics, statistical analyses, baseline derivation, changes from baseline, and any parameter derivations.

8.1.1. Calculation of the Summary Statistics

For continuous data the following rules will be applied:

- Missing values will not be imputed, unless specifically stated otherwise.
- Unrounded data will be used in the calculation of summary statistics.
- If the number of subjects with valid observations (n) <3, summary statistics will not be calculated, with the exception of n, minimum, and maximum.
- As ET data is not associated with any scheduled timepoint, it will be excluded from all calculations of summary statistics.
- Postdose repeats and unscheduled assessments will not be included in calculations of summary statistics.

For categorical data the following rules will be applied:

• If the categories of a parameter are ordered (eg, AE severity), all categories between the possible minimum and maximum categories will be included, even if n = 0 for a

given category. If the categories are not ordered (eg, race), only those categories for which there is at least 1 subject represented will be included.

• Missing values will not be imputed, with the exception of AEs where the 'worst-case' approach will be taken (see Section 8.6.1), or unless specifically stated otherwise. A 'missing' category will be included for any parameter for which information is missing. This will ensure that the population size totals are consistent across different parameters.

All protocol deviations and data issues (eg missing data, out of protocol window) that occur during the study, including those related to COVID-19, will be considered prior to database lock for their severity/impact on how the data will be displayed.

8.1.2. Repeat and Unscheduled Readings

For vital sign measurements and 12-lead ECG data only, any predose value recorded in addition to the original value or a postdose value recorded within 15 minutes of the original value will be defined as a repeat value; any postdose value recorded more than 15 minutes after the original value will be defined as an unscheduled value. For all other data types (eg, laboratory parameters), any value recorded in addition to the original value will be defined as an unscheduled value.

The original scheduled value will be used in all calculations post dose. In the event of any repeats or unscheduled measurements taken pre-dose the values will be considered when determining the baseline value.

Post dose repeats, unscheduled assessments, and ET measurements will be excluded from all calculations, with the exception of the baseline derivation (see Section 0).

8.1.3. Definitions of Baseline and Change from Baseline

Baseline value is defined as the last non-missing measurement before administration of LOXO-305.

If the date/time of the value is incomplete or missing, it will be excluded from the baseline calculation, unless the incomplete date/time indicates the value was recorded prior to dosing.

Individual changes from baseline will be calculated by subtracting the individual subject's baseline value from the value at the timepoint. The mean change from baseline will be defined as the mean of the individual changes from baseline for all subjects.

See Section 8.1.2 for more detail on handling repeat and unscheduled readings in the calculations.

8.2. Subject Disposition and Population Assignment

Subject disposition and population assignment will be listed.

A summary table by renal function group will be provided, based on the all subjects population.

8.3. Demographics and Baseline Characteristics

The demographics and baseline characteristics including age, sex, race, ethnicity, height, body weight, and BMI will be listed.

A summary table by renal function group will be provided, based on the safety population.

The eGFR data will be listed and summarized.

8.4. Prior and Concomitant Medication

Prior medication will be defined as medication that ends prior to the dose of LOXO-305. Concomitant medication will be defined as medication that starts during or after the dose of LOXO-305 or starts but does not end prior to the dose of LOXO-305.

Prior and concomitant medications will be coded using the World Health Organization Drug Dictionary (WHODrug) Global, Format B3, Version September 2020 (or later if upversioned during the study). Prior and concomitant medications will be listed.

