### Safety

All safety assessments, including AEs, SAEs, vital sign measurements, clinical laboratory results, physical examination results, concomitant medications, and 12-lead ECGs, will be tabulated, and summarized where possible, using descriptive methodology by renal function group and, as needed, by timepoint. Unless otherwise specified, baseline value is defined as the last non-missing measurement before administration of LOXO-305. No formal statistical analyses are planned for the safety data. All safety data will be listed by subject.

Additional details on the analyses will be included in the Statistical Analysis Plan.

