#### 2.2.2. Secondary Endpoints

Safety and tolerability will be assessed by monitoring AEs, performing physical examinations and clinical laboratory evaluations, measuring vital signs, and recording ECGs.

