### **8.5. Safety Analysis**

All safety assessments, including AEs, SAEs, vital sign measurements, clinical laboratory results, physical examination results, concomitant medications, and 12-lead ECGs, will be tabulated, and summarized where possible, using descriptive methodology by renal function group and, as needed, by timepoint. Unless otherwise specified, baseline value is defined as the last non-missing measurement before administration of LOXO-305. No formal statistical analyses are planned for the safety data. All safety data will be listed by subject.

Concomitant medications will be coded using the World Health Organization (WHO) Drug Dictionary (WHO Drug Global B3, September 2019). Adverse events will be coded using Medical Dictionary for Regulatory Activities Version (MedDRA) 22.1 (or higher). The incidence of AEs for each renal function group (matched control healthy subjects, mild, moderate, and severe) will be presented by severity and by relationship to study drug as determined by the Investigator or designee ([Appendix 1](#) for AE reporting). All TEAEs will be summarized by system organ class and preferred term, with a breakdown by renal function group.

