1. INTRODUCTION

This SAP has been developed after review of the clinical study protocol (Final Version 2.0 dated 17 February 2021) and electronic case report form.

This SAP describes the planned analysis of the pharmacokinetic (PK), and safety and tolerability data from this study. A detailed description of the planned TFLs to be presented in the clinical study report (CSR) is provided in the accompanying TFL shells document.

In general, the analyses are based on information from the protocol, unless they have been modified by agreement with Loxo Oncology, Inc. A limited amount of information about this study (eg, objectives, study design) is given to help the reader's interpretation. This SAP must be finalized prior to the lock of the clinical database for this study. When the SAP and TFL shells are approved, they will serve as the template for this study's CSR.

This SAP supersedes any statistical considerations identified in the protocol; where considerations are substantially different, they will be so identified. If additional analyses are required to supplement the planned analyses described in this SAP, they may be performed and will be identified accordingly in the CSR. Any substantial deviations from this SAP will be agreed with Loxo Oncology, Inc. and identified in the CSR.

This SAP is written with consideration of the recommendations outlined in the International Conference on Harmonisation (ICH) E9 guideline *Statistical Principles for Clinical Trials* and ICH E3 guideline *Structure and Content of Clinical Study Reports*.^{1,2}

The document history is presented in Appendix 1.

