3.2. Secondary Endpoints

Safety and tolerability will be assessed by monitoring adverse events (AEs) and concomitant medications, performing physical examinations and clinical laboratory evaluations, measuring vital signs, and performing 12-lead electrocardiograms electrocardiogram (ECGs). These safety and tolerability endpoints are deemed adequate to detect any safety signals.

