10. SIGNIFICANT CHANGES FROM THE PROTOCOL-SPECIFIED ANALYSES

There were no significant changes from the protocol-specified analyses.

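### Must the SAP add a by-group table of concomitant medications because Protocol 8.5 promised one?

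*SAP*

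**What the plan says.** Protocol 8.5 names the safety items and how they will be shown: "concomitant medications, and 12-lead ECGs, will be tabulated, and summarized where possible, using descriptive methodology by renal function group". The synopsis makes the same commitment: "physical examination results, concomitant medications, and 12-lead ECGs, will be tabulated, and summarized where possible". Protocol 8.5 then adds a separate requirement: "All safety data will be listed by subject".

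SAP 8.4 defines prior and concomitant medication, says both will be coded with WHODrug, and ends: "Prior and concomitant medications will be listed". It mentions no table. SAP 8.6.5 lists physical examination findings and sends any safety assessment not covered elsewhere to a listing only.

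On how the two documents relate, SAP 1 states: "This SAP supersedes any statistical considerations identified in the protocol; where considerations are substantially different, they will be so identified". SAP 10 states: "There were no significant changes from the protocol-specified analyses". SAP 1 also says that the detailed description of the planned tables, figures and listings is in a separate shells document.

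**The concern.** Read side by side, the documents promise different things. The protocol treats tabulation and listing as two commitments, and SAP 8.4 keeps one. Because the SAP says that it overrides the protocol, the listing-only plan would govern, and SAP 10 would not tell the reader that a summary had been dropped.

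The SAP also seems to pull in two directions. Protocol 2.2.2 leaves medications out of the safety measures: "Safety and tolerability will be assessed by monitoring AEs, performing physical examinations and clinical laboratory evaluations, measuring vital signs, and recording ECGs". SAP 3.2 puts them in: "Safety and tolerability will be assessed by monitoring adverse events (AEs) and concomitant medications". Yet no SAP section summarises them.

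The subject matter gives this some weight. Protocol 6.1 and exclusion criteria 15 and 38 let renally impaired subjects stay on approved stable medication, while controls have only the general waiver. Medication use can therefore differ between the groups being compared. It is not a matching factor, and LOXO-305 is metabolised mainly by CYP3A4 among the CYP enzymes (Protocol 1.2) and is a P-gp and BCRP substrate (Protocol 1.3). A reader of the renal comparison could fairly ask what each group was taking.

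**Working it through.** No figure in the plan is at issue, so the check is a comparison of text followed by a look at what the missing output could affect.

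**1. What the SAP does with each safety item named in Protocol 8.5**

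| Item | SAP section | Presentation |
|---|---|---|
| AEs | 8.6.1 | Summarised by group, and listed |
| SAEs | 8.6.1 | Summarised by group, and listed |
| Vital signs | 8.6.3 | Summarised by group and timepoint, and listed |
| 12-lead ECGs | 8.6.4 | Summarised by group and timepoint, and listed |
| Laboratory results | 8.6.2 | Chemistry, hematology and coagulation summarised; urinalysis listed |
| Physical examination | 8.6.5 | Listed |
| Concomitant medications | 8.4 | Listed |

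Of the seven items, four are fully summarised, one is partly summarised and two are listed.

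**2. Whether *listed* could mean *tabulated*.** Not comfortably. The protocol asks for the listing in its own sentence. SAP 8.2 and 8.3 first list and then add a summary table by renal function group, and SAP 8.4 has no such addition. Listing-only is the likelier reading of the SAP text. It is not certain, because the shells hold the detailed output plan and were not available.

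**3. Whether the analysis depends on the table.** The primary comparison (Protocol 8.4.2, SAP 8.5.3) uses paired t-tests on ln-transformed AUC0-t, AUC0-inf and Cmax. The ANCOVA uses renal function group, sex, age and BMI. Medication is in neither, and SAP 8.6.6 plans no inference on safety data. With or without the table, every ratio, interval and adverse event count is the same.

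**4. Whether information is lost.**
- The missing table would cover at most 8 + 8 = 16 dosed subjects in the first stage, and at most 24 + 24 = 48 if Groups 2 and 3 open.
- The medications are coded (SAP 8.4), so like drugs can be grouped.
- The listing runs over everyone who signed consent and had an assessment recorded (SAP 7.1 and 8.1), so it must be cut down to dosed subjects. Population assignment is also listed (SAP 8.2), and the subject number shows the renal function group (Protocol 4.5).
- All PK parameters are listed (SAP 8.5.3), and the matched pairs will be listed in the study report (Protocol 4.7). A reader who suspects that a drug affected exposure can trace it to one subject, that subject's AUC and that subject's match. A group count cannot do this.

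**5. Whether SAP 10 is wrong.** SAP 1 asks for substantial differences to be identified, and SAP 10 denies only significant ones. A descriptive count that feeds no estimate and can be rebuilt from planned output can reasonably be judged neither.

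**The case for a change.** The best case for a change is that it would be cheap. One sentence in SAP 8.4 and one table from data already coded would keep the protocol's promise; one sentence in SAP 10 would at least declare the departure. The *where possible* qualifier does not excuse the gap: it attaches to summarising rather than tabulating, and coded medications can be counted. Medication use is also a factor on which the groups may well differ, whereas age, sex and BMI, which SAP 8.3 does tabulate, are already matched.

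The textual part of this stands: the protocol promised more than the SAP text delivers, and the SAP does not say so. The rest is weaker.

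- The contrast with SAP 8.3 is selective. That section also tabulates race, ethnicity, height and weight and summarises eGFR, so it is not confined to matched factors.
- SAP 3.2 speaks of monitoring medications. Recording and listing them is consistent with that, and the sentence promises no table.
- A medication table alone would not bring the documents into line, because physical examination and urinalysis would still be listed only. For physical examination little is lost: findings that are adverse events are recorded as such (Protocol 7.2.1), and treatment-emergent events are summarised by group.
- A table that mixed in prior medication could mislead. Appendix 4, footnote q, adds a 30-day look-back for prescription drugs in renally impaired subjects only, so prior-use counts would not be like for like.

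Low cost is not a gain in itself. The table would change no number, precision, bias or safety conclusion.

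**Conclusion.** The mismatch is real but has no consequence for the trial's answer, so no change follows. Two named safety items, and the urinalysis part of a third, are listed where the protocol spoke of tabulation by group. The effect on every PK ratio, confidence interval and adverse event summary is nil. The information remains available subject by subject for at most 16 dosed subjects, or 48 if all groups open, and at that size a listing that can be tied to individual exposures and matched pairs serves the reader at least as well as a count.

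This conclusion assumes that the listings are produced as SAP 8.1, 8.2 and 8.4 describe and that medication is not brought into the PK models. It does not depend on the shells: if they contain the table, the gap exists only in the SAP's wording; if they do not, nothing estimated is affected. A team that wants the count for the study report can produce it, since SAP 1 allows supplementary analyses that are identified as such.

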8.5. Pharmacokinetic Assessments

8.5.1. Pharmacokinetic Analysis

The following PK parameters will be determined where possible from the plasma concentrations of LOXO-305 using noncompartmental methods in validated software program Phoenix WinNonlin (Certara, Version 8.1 or higher):

Parameter	Units ^a	Definition
AUC _{0-t}	h*ng/mL	area under the concentration-time curve from hour 0 to the last measurable concentration $(t_{last})^b$
AUC _{0-inf}	h*ng/mL	area under the concentration-time curve from time 0 extrapolated to infinity ^c
%AUC _{extrap}	%	percentage extrapolation for AUC _{0-inf}
C_{max}	ng/mL	maximum observed plasma concentration
t _{max}	h	time to maximum observed plasma concentration
λ_z	1/h	apparent terminal elimination rate constant
t _{1/2}	h	apparent terminal elimination half-life
CL/F	L/h	apparent systemic clearance
V_z/F	L	apparent volume of distribution at the terminal phase
MRT_{inf}	h	mean residence time (based on AUC _{0-inf})
\mathbf{f}_{u}		unbound fraction

^a Units are based on concentration units (provided by the bioanalytical lab or preferred units for presentation of PK parameters) and dose units used in the study.

^b Area under the concentration-time curve will be calculated using the linear trapezoidal rule for increasing and decreasing concentrations

^c Based on the last observed quantifiable concentration

The unbound fraction (f_u) in plasma, expressed as a decimal, will be calculated from protein binding concentration data as the unbound drug concentration divided by the total drug concentration in plasma. The f_u value determined for each subject will be used to calculate the following unbound LOXO-305 PK parameters for each individual subject:

C _{max,u}	Unbound C_{max} , calculated as $C_{max}*f_u$
AUC _{0-t,u}	Unbound AUC _{0-t} , calculated as $AUC_{0-t}*f_u$
AUC _{0-inf,u}	Unbound AUC _{0-inf} , calculated as $AUC_{0-inf}*f_u$
CL/F,u	Unbound CL/F, calculated as Dose/AUC _{0-inf,u}
V _z /F, _u	Unbound V _z /F, calculated as CL/F, _u / λ_Z

Additional PK parameters may be determined where appropriate.

The PK analysis will be carried out where possible using actual blood sampling times postdose. If an actual time is missing, the sample concentration result will be treated as missing unless there is scientific justification to include the result using the nominal time.

The parameters C_{max} and t_{max} will be obtained directly from the concentration-time profiles. If C_{max} occurs at more than 1 timepoint, t_{max} will be assigned to the first occurrence of C_{max} .

8.5.1.1. Criteria for the Calculation of Apparent Terminal Elimination Rate Constant and Half-life

The start of the terminal elimination phase for each subject will be defined by visual inspection and generally will be the first point at which there is no systematic deviation from the log-linear decline in concentrations.

The apparent terminal elimination rate constant (λ_z) will only be calculated when a reliable estimate can be obtained using at least 3 data points, preferably not including C_{max}, and the adjusted coefficient for determination of exponential fit (R²-adj) of the regression line is ≥ 0.7 . Parameters requiring λ_z for their calculation (eg, AUC_{0-inf}, t_{1/2}, CL/F, V_z/F, and MRT_{inf}) will only be calculated if the R²-adj value of the regression line is ≥ 0.7 .

The following regression-related diagnostic PK parameters will be determined, when possible:

Parameter	Units	Definition
λ_z Upper	h	end of exponential fit
λ_z Lower	h	start of exponential fit
$\lambda_z N$	NA	number of data points included in the log-linear regression
λ_z Span Ratio	NA	time period over which λ_Z was determined as a ratio of $t_{1/2}$
R ² -adj	NA	adjusted coefficient for determination of exponential fit

Where possible, the span of time used in the determination of λ_z (ie, the difference between λ_z Upper and λ_z Lower) should be ≥ 2 half-lives. If the λ_z Span Ratio is <2, the robustness of the t_{1/2} values will be discussed in the CSR.

